Six-Minute Walk Test		X	X	X
Short Physical Performance Battery		X	X	X
QoL Questionnaires		X	X	X
Health Literacy Questionnaire		X		
Echocardiogram		X		X
^{99m} Tc-PYP Scintigraphy**		X		
Phone Call Follow-Up [¶]			X	X

* Follow-up visits are to be conducted on subjects who test positive to the Cardiac Amyloid Scintigraphy scan and/or are carrier of the V122I mutation. Window for the 6-month visit is ±2 weeks and for the 12-month visit is ±4 weeks.

† Height measured only at baseline visit. Subjects with weight >350 lb will not participate in the study.

‡ Includes BNP, NT-proBNP, galectin-3, troponin I and T.

§ Includes Vitamin A and RBP4 in on site spot urine.

¶ For participants with no TTR CA, a phone call follow-up will be conducted instead.

**In the event that PYP is unavailable due to supply shortage, the investigator has the option of using HDP until PYP becomes available again to ensure study continuation per FDA.

For every study visit, a checklist will be used to help ensure completion of all the study procedures. The checklist is also a guide that suggests the order in which the assessments should be performed (See [Appendix 3](#)).

TABLE OF CONTENTS

STUDY SYNOPSIS.....	2
LIST OF ABBREVIATIONS AND DEFINITIONS OF TERMS.....	9
1. INTRODUCTION	10
1.1 Background and Rationale	10
1.1.1 Transthyretin Biology	10
1.1.2 Transthyretin-mediated amyloidosis definition	10
1.1.3 Pathogenesis and Outcome.....	11
1.1.4 ATTR-CM and Heart Failure	11
1.2 ATTR-CM Population Burden.....	13
1.2.1 ATTR amyloid is an under-recognized cause of heart failure	13
1.2.2 Are Hispanics affected by TTR-CA?	14
1.2.3 TTR-CA from mutant protein has more severe phenotype than wild type	14
1.3 Natural History of Transthyretin Cardiac Amyloidosis	15
1.3.1 Clinical Characteristics and Outcome in ATTR-CA in TRACS	15
1.3.2 Predictors of Mortality	16
1.4 Therapeutic Options.....	17
1.4.1 Novel Therapies Require Early Identification of Affected Individuals	17
1.4.2 Tc-PYP & Tc-HMDP can detect TTR-CA without the need for an amyloid biopsy	
18	
1.4.3 Myocardial retention of Tc99-PYP is prognostic in TTR-CA	18

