Hypothesis 4. Progression of disease: Markers of disease progression are lacking in ATTR CA. We hypothesize that attainment of a hierarchical composite endpoint at 1-year of death, heart failure hospitalization, and 30% decline in 6-minute hall walk will be higher in ATTRm vs. ATTRwt CA. In addition, we will explore the capacity of specific markers to assess disease progression including: (1) established circulating biomarkers such as troponin I/T, NT-proBNP, BNP and Galectin-3, (2) novel biomarkers such as RBP4 and TTR concentration, (3) ECG, and

echocardiographic measures including longitudinal strain and MCF, (4) functional capacity by 6-minute hall walk and SPPB, and (5) QOL. Our preliminary data and published work⁹ suggests reduced median survival for ATTRm Val122Ile CA (25 months) vs ATTRwt (43 months) in different race cohorts. We hypothesize that we will observe reduced survival and greater functional decline in ATTR Val122Ile vs ATTRwt within race cohorts.

Hypothesis 5. Performance of risk calculator: Our point-of-care risk calculation utilizing RBP4 and TTR concentration with echocardiographic and ECG determined parameters will be tested in this cohort. We will re-derive the prediction model based upon clinical variables noted above. We anticipate showing a similar degree of accuracy (ROC AUC > 0.95) for identification of cases with ATTR vs. controls

Specific Aim 2: To demonstrate that circulating RBP4 concentration is integral to TTR tetramer stability, which in turn determines the clinical characteristics of ATTR CA. We will measure TTR tetramer stability and RBP4 concentration in serum and urine collected in Aim 1. The overall hypotheses of this Aim are that measurements of TTR kinetic stability, RBP4 and TTR concentration will differentiate patients with ATTR CA vs. non-amyloid HF controls and associate with disease progression and outcomes. Specific hypotheses are as follows:

Hypothesis 1: TTR kinetic stability and RBP4 concentration: We hypothesize that at baseline, TTR kinetic stability will be lower in ATTR CA vs. non-amyloid HFpEF, and that stability will be inversely proportional to plasma RBP4 concentration. We further hypothesize that TTR kinetic stability will be lower for ATTRm vs. ATTRwt.

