2.1.7 Statistical Considerations and Sample Size

Power and Sample Size: The total enrollment proposed for this study is of 800 subjects: 600 Blacks and 200 Hispanics. Amongst them, we expect approximately 80-160 ATTR CA subjects and 640-720 non-amyloid controls. The sample size planned for each race/ethnicity group achieves 80% power to

detect, as in Aim 1: (1) a prevalence of ATTR-CA of 10-15%, (2) a two-fold difference in the prevalence of ATTRm between Blacks and Hispanics (i.e., 0.08 vs 0.04, respectively), as well as, a similar difference in the prevalence of ATTRwt between Blacks and Hispanics, (3) a difference as small as 0.03 (if one truly exists) in the prevalence of ATTRwt with respect to gender (male) distribution between the two race/ethnic groups, and (4) in the ATTR CA group alone, we plan to measure the hierarchical composite endpoint of death, heart failure hospitalization, and 30% decline in 6-minute hall walk after 1 year. A two-sided logrank test with an overall sample size of 80 subjects (40 in the ATTRwt and 40 in the ATTRm) achieves 82% power at a 0.05 significance level to detect a hazard ratio (HR) of 0.44 when the proportion of patients that did not progress in the mutant group is 0.60. This corresponds to a minimum difference of 15% in the probability of not having progressed past 12 months between the two groups.

Aim 2 focuses on comparing differences in TTR kinetic stability and RBP4 concentration between ATTR CA (N=80-120) and the non-amyloid group (N=680-720). These sample sizes generate >95% power to detect: Hypothesis 1) a minimum difference in RBP4 of 5, assuming SDs of 9 and 20 for ATTR CA and non-amyloid, respectively; Hypothesis 2) a mean change difference in TTR stability as small as 0.01, SD of 0.002.

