Ventricular Rate(bpm) _____

Total QRS Voltage (mm) _____

PR Interval (msec) _____

Low QRS Voltage Yes No

QRS Axis (degrees) _____

QT Interval (msec) _____

QRS Duration (msec) _____

QTc Interval (msec) _____

SV₁ + RV₅ or V₆ (mm) _____

Overall Assessment

Rhythm

Sinus Rhythm Atrial Fibrillation

Ventricular Conduction Defect Yes No

Other, specify: _____

If yes, Left Bundle Branch Block

Electrical Pacing on ECG Yes No

Incomplete Left Bundle Branch Block

If yes, Atrial Pacing

Left Anterior Hemiblock

Ventricular Pacing

Left Posterior Hemiblock

Atrial Ventricular Pacing

Right Bundle Branch Block

ST or T-wave changes Yes No

Incomplete Right Bundle Branch Block

If yes, specify reason:

Intraventricular Conduction Delay

A-V Block Yes No

Infarct pattern/Poor R-wave progression Yes No

If yes, 1st degree

If yes, infarct pattern is observed in this locations:

2nd degree, Type I

Anteroseptal

2nd degree, Type II

Anterior

3rd degree heart block

Anterolateral

Other, specify: _____

Lateral

Inferior

Other, specify: _____

Form Completed by: _____ Investigator's Signature: _____

SHORT PHYSICAL PERFORMANCE BATTERY (SPPB)**1. Balance Tests****a. Side-by-Side Stand**

Held for 10 s → 1 point
 Not held for 10 s Time: ____ . ____ s → 0 points, go to #2
 Not attempted

b. Semi-Tandem Stand

Held for 10 s → 1 point
 Not held for 10 s Time: ____ . ____ s → 0 points, go to #2
 Not attempted

c. Tandem Stand

Held for 10 s → 2 point
 Held for 3 to 9.99 s → 1 point
 Held for < than 3 s → 0 points
 Not attempted

d. Balance Ordinal Score: ____ (sum points)

If not attempted, select reason:

1 Tried but unable
2 Participant could not hold position unassisted
3 Not attempted, you felt unsafe
4 Not attempted, participant felt unsafe
5 Participant unable to understand instructions
6 Other (specify): _____
7 Participant refused

2. Gait Speed Test**a. Test #1**

Time for 4-meter: ____ . ____ s

b. Test #2

Time for 4-meter: ____ . ____ s

c. Walking aid None Cane Walker**d. Record best of the two times**

Best time: ____ . ____ s

If not attempted, select reason:

1 Tried but unable
2 Participant could not walk unassisted
3 Not attempted, you felt unsafe
4 Not attempted, participant felt unsafe
5 Participant unable to understand instructions
6 Other (specify): _____
7 Participant refused

e. Gait ordinal score: ____

Could not do

>8.70 s

6.21-8.70 s

4.82-6.20 s

<4.82 s

3. Repeated Chair Stand Test**a. Safe to stand five times?**

Yes No

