b. If five stands done, record time:

Time to complete five stands: ____ . ____ s

c. Chair stand ordinal score: ____

Unable to complete 5 chair stands or completes stands in >60 s

If chair stand time is ≥ 16.70 s and ≤ 60 s

If chair stand time is ≥ 13.70 s and < 16.70 s

If chair stand time is ≥ 11.20 s and < 13.70 s

If chair stand time is < 11.20 s

If not attempted, select reason:

Tried but unable

Participant could not stand unassisted

Not attempted, you felt unsafe

Not attempted, participant felt unsafe

Participant unable to understand instructions

Other (specify): _____

Participant refused

4. Total Score

Points: ____ (sum of scores above)

Form Completed by: _____

SIX-MINUTE WALK TEST

PROMPT: "The object of this test is to walk as far as possible for 6 minutes. You will walk back and forth in this hallway. You will probably get out of breath or become exhausted. You are permitted to slow down, to stop, and to rest as necessary. You may lean against the wall while resting, but resume walking as soon as you are able. You will be walking back and forth around the cones. You should pivot briskly around the cones and continue back the other way without hesitation."

Answer any questions the participant may have.

PROMPT: "Are you ready to do that? Remember that the object is to walk AS FAR AS POSSIBLE for 6 minutes, but don't run or jog. Start now, or whenever you are ready."

1. Is participant using an assistive device? No Yes

If "Yes" ... Cane Walker

2. Supplemental oxygen during the test? No Yes

3. Measurements

	Baseline	End of Test
--	-----------------	--------------------

Time ____ : ____

Heart Rate (bpm) ____

SpO₂% ____

Borg Scale

Dyspnea ____

Fatigue ____

4. Stopped or paused before 6 minutes? No Yes

Reason: _____

5. Symptoms at end of exercise (select all that apply):

- Angina
- Dizziness
- Hip pain
- Leg pain
- Calf pain
- Other (specify): _____

6. Total distance walked in 6 minutes: ____ meters

Form Completed by: _____

THE KANSAS CITY CARDIOMYOPATHY QUESTIONNAIRE (KCCQ)

The following questions refer to your **heart failure** and how it may affect your life. Please read and complete the following questions. There are no right or wrong answers. Please mark the answer that best applies to you.

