Time between injection and acquisition: (ideally 3 hrs)
____ : ____ (hh:mm)Image duration: _____ counts
(750,000 minimum counts)**Adverse Reactions (AR)**Any AR to radiotracer injection? Yes No

If 'Yes', please check all that apply:

 Flushing Itching Hypotension Skin rash Fever Chest pain Chills Palpitations Nausea Tachycardia Vomiting Shortness of breath Dizziness Other (specify): _____**Difficulties with Scan**

Please note any difficulties in obtaining the scan. For example, difficulty positioning the participant, participant motion, etc. and any action taken to correct it.

Form Completed by: _____

CARDIAC AMYLOID SCINTIGRAPHY Findings Sheet**Nuclear Findings****Planar myocardial radiotracer uptake pattern:**

 Absent	 Diffuse
 Focal	 Focal on diffuse

Semi-quantitative visual grading of radiotracer uptake – based on “Planar” images:

- Grade 0: no uptake and normal bone uptake
- Grade 1: uptake less than rib uptake
- Grade 2: uptake equal to rib uptake
- Grade 3: uptake greater than rib uptake with mild/absent rib uptake

Was SPECT imaging performed? Yes No

If 'Yes':

Semi-quantitative visual grading of radiotracer uptake – based on “Planar” and “SPECT” images:

- Grade 0: no uptake and normal bone uptake
- Grade 1: uptake less than rib uptake
- Grade 2: uptake equal to rib uptake
- Grade 3: uptake greater than rib uptake with mild/absent rib uptake

Quantitative interpretation of radiotracer uptake:

H/CL ratio: ____ . ____

If SPECT or SPECT/CT done, blood pool activity:

- Absent
- Minimal
- Significant

Technical Findings**Study difficulties:**

- None
- Participant motion
- High background
- Inadequate count density
- Dose infiltration
- Delay in imaging
- Poor labeling
- Other, specify: _____

Artifact Findings**Incidental Findings***(Bone findings, hot spots, pleural or pericardial effusion, etc.)***Comments****Conclusion****Overall interpretation:**

- Not suggestive of ATTR
- Strongly suggestive of ATTR
- Equivocal for ATTR / Possible early ATTR

Study quality:

- Uninterpretable
- Poor
- Fair
- Good
- Excellent

ON-SITE FOLLOW-UP

1. Was the study visit conducted? Yes No

a. If no, did the patient drop out of the study? Yes No

If yes, date of drop out: ____ / ____ / _____

If yes, provide reason subject dropped out, and **go to #2**:

b. If no, did the subject die? Yes No

If yes, date of death: ____ / ____ / _____

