Is death related to study participation? Definitely Possibly Not related

If yes, provide description/narrative, and **go to #2**:

c. If no, provide reason subject missed visit:

2. Has the patient been hospitalized? Yes No

If yes, number of hospitalizations: ____

If yes,

Reason	Causality			Hospital	Date of admission	Date of discharge
	HF	CVA	Other CVD			
1						
2						
3						
4						
5						

3. Was the patient seen in the ER? Yes No

If yes, number of ER visits: ____

If yes,

Reason	Causality			Hospital	Date of admission	Date of discharge
	HF	CVA	Other CVD			
1						
2						
3						
4						
5						

4. Has the patient had any ambulatory procedures/interventions (no overnight stay) Yes No

If yes, number of procedures ____

If yes,

Visit: **6M** **12M**

Date of Visit: ____ / ____ / _____

Study ID#: _____

Reason	Causality			Hospital	Date of procedure
	HF	CVA	Other CVD		
1					____ / ____ / ____
2					____ / ____ / ____
3					____ / ____ / ____
4					____ / ____ / ____
5					____ / ____ / ____

5. Has the patient been infected with COVID-19? Yes No

If yes, date of COVID-19 diagnosis: ____ / ____ / _____

Visit: **6M** **12M**

Date of Visit: ____ / ____ / _____

Study ID#: _____

Form Completed by: _____ Investigator's Signature: _____

PHONE CALL FOLLOW-UP1. Was any data collected? Yes NoIf yes, Phone Chart review Phone and chart review

If no, reason: _____

If no, deceased? Yes No

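### Deaths after drop-out are not reliably captured in ATTR-CA cases, and a walk not attempted has no code or rule, so the ATTRm v ATTRwt composite is open to informative loss of events

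*Combined protocol and SAP*

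**What the plan says.** Section 2.1.6 (Aim 1, Hypothesis 4) compares ATTRm with ATTRwt on "attainment of a hierarchical composite endpoint at 1-year of death, heart failure hospitalization, and 30% decline in 6-minute hall walk". Section 2.1.8 makes Kaplan-Meier and Cox the main analysis, with Finkelstein-Schoenfeld and the win ratio as alternatives that put mortality first.

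Data collection runs through the forms in Appendix 4:

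- **On-site follow-up form, item 1.** If the visit was not held, the form asks whether the participant dropped out. "If yes, provide reason subject dropped out, and" is followed by a jump to item 2 (hospitalizations). The death question, "If no, did the subject die", is reached only when the drop-out answer is no.
- **Phone form, item 1.** The form allows phone, chart review or both. Its death question, "If no, deceased", sits in the branch for no data collected.
- **Who gets the phone form.** The Schedule of Activities and Table 4 say "For participants with no TTR CA, a phone call follow-up will be conducted instead". Section 2.1.5.8 describes the group with an and/or that joins absence of TTR CA to non-carrier status, and says the contact gathers vital status.
- **Walk form.** It records "Total distance walked in 6 minutes" and any early stop or pause, but has no code for a test not attempted. The SPPB form, used at the same visits, does have reason codes, including "Participant could not walk unassisted".

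Section 2.1.8 gives no rule for drop-outs, missing walks or inability to walk. The only censoring rule, in section 2.2, covers entry into an investigational trial.

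**The concern.** Death is the most important component, and a case who leaves the study is the one whose death the on-site form does not ask for. Cases who leave or who cannot walk may well be sicker than those who stay. If so, the missing events are not a random subset, and progression is understated. If the loss is proportionally greater in ATTRm, the contrast with ATTRwt shrinks. The prioritised analyses are also exposed, because they compare participants on survival first.

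**Working it through.** **1. Routes by which a case's death could be recorded**

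- *Case misses the visit, not coded as a drop-out:* the on-site form reaches the death item. Captured.
- *Case coded as a drop-out, then dies:* the on-site form skips the death item. Hospitalizations are still asked.
- *Phone or chart review for that case:* not provided by the Schedule of Activities or Table 4. The and/or in 2.1.5.8, read literally, could admit ATTRwt cases (non-carriers) but not ATTRm cases. That would make follow-up unequal between the two groups compared, so the wording needs settling.
- *Death found by chart review on the phone form:* data were collected, so the death item is not reached, despite the vital-status purpose in 2.1.5.8.
- *SAE form, Part C:* has date and place of death. But section 3.2 defines SAEs as related to participation, and section 3.3 ends AE recording 48 hours after the tracer. Entry of an unrelated later death is possible, not required.
- *Electronic record:* section 3.3 names it as a source, but its findings go onto the same forms.

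**2. The plan's own figures**

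Inputs (2.1.7): 40 + 40 cases, HR 0.44 (ATTRwt relative to ATTRm), 12-month progression-free proportion 0.60 in ATTRm, two-sided alpha 0.05, stated power 82%.

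- ATTRwt progression-free = 0.60^0.44 = 0.799.
- Expected events = 40 × 0.40 + 40 × 0.201 = 24.1.
- Schoenfeld power = Φ(|ln 0.44| × √(24.1/4) − 1.96) = 52%.

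The 82% is not reproduced; 80 *per group* gives 81%. That is a separate matter and does not decide this point. What matters here is that only about 24 events are expected.

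**3. Expected deaths**

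Medians of 25 months (ATTRm) and 43 months (ATTRwt) come from Hypothesis 4; a constant hazard is assumed.

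- ATTRm: 1 − 2^(−12/25) = 0.283; × 40 = 11.3 deaths.
- ATTRwt: 1 − 2^(−12/43) = 0.176; × 40 = 7.0 deaths.
- If 10% to 20% of the 18.3 deaths follow a drop-out (assumption), 1.8 to 3.7 are at risk of being missed.

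**4. Effect of losing events**

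The documents give no loss rate, so q = 10% / 20% / 30% of events is an assumed range. If a share q of those about to have an event leave just before it and are censored, the observed hazard is multiplied by (1 − q).

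- ATTRm progression-free at 12 months = 0.60^(1 − q) = 0.63 / 0.66 / 0.70 instead of 0.60. Simulation gave 0.632 / 0.664 / 0.700.
- Same q in both groups: (1 − q) cancels and the HR stays at 0.44.
- Loss in ATTRm only: HR = 0.44/(1 − q) = 0.49 / 0.55 / 0.63.

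For comparison, if the same people were instead counted as event-free to month 12:

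- ATTRm progression-free = 1 − 0.40(1 − q) = 0.64 / 0.68 / 0.72.
- HR with equal loss = 0.448 / 0.455 / 0.462.
- HR with loss in ATTRm only = 0.50 / 0.58 / 0.68.

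The direction is the same, and the bias in the progression-free proportion is slightly smaller under censoring.

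**The case against.** The best defence is that the forms are less leaky than the skip suggests. SAE form Part C has fields for a fatal event, item 12 allows it to be marked as not caused by the study, and the Adverse Events Log offers grade 5 with no relation to the study. A case too ill to walk who has not dropped out still reaches the death item, and drop-outs are still asked about hospitalization. The month 6 and month 12 checklists have a not-done box and notes for the walk. Equal proportional loss hardly moves the hazard ratio. If the phone form serves only participants without TTR CA, its gap cannot affect a composite measured in cases alone.

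Most of this stands, and it limits the point. What it does not answer is that sections 3.2 and 3.3 do not require an unrelated late death to be entered, so the endpoint depends on sites going beyond the stated rules. Free-text notes without an analysis rule do not define an event. The phone form's gap matters once that form is used as the fallback for cases.

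A reader might infer that drop-outs and cases too ill to walk are carried as event-free. The documents do not say so: the plan is silent, the on-site form records a drop-out date, and Kaplan-Meier and Cox would usually censor. Nor do they show that ascertainment is weaker in cases than in phone-followed controls, since the controls' form has its own gap for deaths.

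**Conclusion.** The concern holds in this form: as the forms and sections 3.2 and 3.3 are written, deaths after drop-out can be missed in the ATTRm v ATTRwt composite, and no fallback contact is clearly stated for scan-positive participants who leave. The usual handling would be censoring, probably informative, which understates progression. Bias of the hazard ratio toward no difference needs greater proportional loss in ATTRm. That is plausible, because the protocol expects ATTRm to do worse, but it is not shown.

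The size is unknown. The figures above rest on assumed loss rates, constant hazards and departure just before the event. They also overstate the loss wherever a lost death followed an HF hospitalization that already counted. With about 24 expected events, even two to four missed deaths would be noticeable.

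The walk component is secondary: a case too ill to walk has no distance, so cannot meet a 30% decline, and no rule says how that case is treated.

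**What to change.** 1. **On-site form:** ask vital status and date of death for every participant, whatever the drop-out answer.
2. **Phone form:** move the death question and date out of the branch for no data collected.
3. **Section 2.1.5.8:** resolve the and/or, and state that scan-positive participants and carriers who stop attending, and have not withdrawn permission for record use, are followed with the existing phone/chart-review form at 6 and 12 months. Consent pages are not in the public text, so the permission terms need checking.
4. **Sections 3.2 and 3.3:** reconcile with the SAE form and Adverse Events Log, so it is clear where an unrelated death is recorded.
5. **Section 2.1.8:** state the censoring rule for drop-outs. Prespecify the handling of a walk not done, using the SPPB not-attempted codes and checklist notes. One option is to count inability for cardiac or functional reasons as meeting the decline, with a sensitivity analysis treating it as missing.

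The cost is edits to two forms, short text changes and a few extra chart reviews, which can also be done retrospectively for cases already lost where permission allows. The downside is a slightly less objective walk component, because it would rely on a reason code.
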